8.3 Safety Analysis

All safety analyses will be based on the Safety Population.

8.3.1 Adverse Events

All the adverse events (AEs) reported throughout the study will be coded and classified according to the MedDRA (Medical Dictionary for Regulatory Activities) coding dictionary (Version 20.0 or higher). Each adverse event is to be evaluated for date of start and end, seriousness, severity, causal relationship with the study drugs, action taken and outcome.

The total number and percentage of patients with at least one AEs, discontinued study drug due to AEs, AE severity and AEs related to investigational product, serious AEs and death will be summarized by treatment groups.

A summary table of the number and percent of patients with AEs by system organ class, preferred term, and treatment group will be presented. Each patient will be counted only once within each preferred term.

A frequency summary table of the number of AEs by system organ class, preferred term, severity, and treatment group will be presented. Severity will be classified as “Mild”, “Moderate”, or “Severe”.

Similarly, a frequency summary table of the number of AEs by system organ class, preferred term, and relationship to a study drug, and treatment group will be presented. Relationship to a study drug will be classified as “Related” or “Not Related”.

Adverse event frequencies will be compared between treatments using Fisher’s exact test. If the overall Fisher’s test is statistically significant, a pairwise test will be conducted for Test and Reference to determine if the difference in AEs is related to the active product.

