5.0 SYNOPSIS

Protocol Number	71691702
Title	A Randomized, Double-Blind, Placebo-Controlled, Parallel-Design, Multiple-Site Clinical Study to Evaluate the Therapeutic Equivalence and Safety of Ivermectin Lotion 0.5% (Actavis Laboratories UT, Inc.) to SKLICE® (ivermectin) Lotion, 0.5% (Arbor Pharmaceuticals, LLC) in the Treatment of Human Head Lice Infestation
Objectives	
The objectives of this study are to:
 
1. Evaluate the therapeutic equivalence of the Test formulation, Ivermectin Lotion 0.5% (Actavis Laboratories UT, Inc.) to the Reference product, SKLICE® (ivermectin) Lotion, 0.5% (Arbor Pharmaceuticals, LLC) in the treatment of active head lice infestation.2. Demonstrate the superiority of the Test and Reference (active) treatments over Placebo treatment in patients with active head lice infestation.3. Compare the safety of Test, Reference and Placebo treatments in patients with active head lice infestation.
Sponsor	Actavis LLC
Study Products	
• Test: Ivermectin Lotion, 0.5% (Actavis Laboratories UT, Inc.)• Reference: SKLICE® (ivermectin) Lotion, 0.5% (Arbor Pharmaceuticals, LLC)• Placebo: Placebo (vehicle) lotion (Actavis Laboratories UT, Inc.) 
Study products will be supplied in 4 oz (117 g) tubes.

Dosage Regimen	Patients will be instructed to administer a single application of study product to the hair on Day 1.
Route of Administration	Topical
Treatment Randomization	[REDACTED]
Patient Population	Male and female patients, 6 months of age and older, with active Pediculus humanus capitis (human head lice) infestation, of which approximately 378 are expected to be index patients.
Study Design	Randomized, double-blind, placebo-controlled, parallel-design, multiple-site bioequivalence study with clinical endpoints
Study Conduct	Eligible patients will be randomized [REDACTED] to one of three treatments (Test, Reference or Placebo) at Visit 1. All members of the household will be examined for lice, [REDACTED]

CONFIDENTIAL PROTOCOL

A Randomized, Double-Blind, Placebo-Controlled, Parallel-Design, Multiple-Site Clinical Study to Evaluate the Therapeutic Equivalence and Safety of Ivermectin Lotion 0.5% (Actavis Laboratories UT, Inc.) to SKLICE® (ivermectin) Lotion, 0.5% (Arbor Pharmaceuticals, LLC) in the Treatment of Human Head Lice Infestation

Patients

will

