10.3.2 Exclusion Criteria

1. Females who are pregnant, lactating or planning to become pregnant during the study period.

CONFIDENTIAL PROTOCOL

A Randomized, Double-Blind, Placebo-Controlled, Parallel-Design, Multiple-Site Clinical Study to Evaluate the Therapeutic Equivalence and Safety of Ivermectin Lotion 0.5% (Actavis Laboratories UT, Inc.) to SKLICE® (ivermectin) Lotion, 0.5% (Arbor Pharmaceuticals, LLC) in the Treatment of Human Head Lice Infestation

2. Patients who do not have a known household affiliation with their household members (i.e., do not stay in one household consistently, sleeping at one place several nights and then at another place or location). Household is defined as living in a shared area or space (for example the same house or apartment unit).
3. Any infested member of the household is unable or unwilling to be treated with the study product. This includes male heads of household who do not attend Visit 1 but report infestation with lice.
4. More than three members of the household infested with lice.
5. Presence of visible skin/scalp condition(s) or open wounds at the application site that are not attributable to head lice infestation and that in the opinion of the Investigator will interfere with safety and/or efficacy evaluations.
6. Presence of eczema or atopic dermatitis at the application site.
7. Use of any prescription, OTC, or home remedies for the treatment of head lice within 7 days before Visit 1.
8. Use of pediculicides within 4 weeks before Visit 1.
9. Use of systemic anti-parasitic agents within 4 weeks before Visit 1.
10. Patients with very short (shaved) hair or who are planning to shave head during the study.
11. Use of any hair dye, bleaches, hair straightening or permanent wave solution on the hair within 14 days before Visit 1.
12. History of allergy or sensitivity to pediculicides or hair care products.
13. History of any drug hypersensitivity or intolerance that, in the opinion of the Investigator, would compromise the safety of the patient or results of the study.

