11.3.3 Safety Populations

The Safety population will include all patients who are randomized and received study product.

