4. RANDOMIZATION AND BLINDING

The study product will be randomized, packaged and blinded by an independent packaging company (Actavis, SLC site). The randomization will be pre-planned according to a computer-generated randomization schedule. All enrolled members of a household will be randomized to the same treatment arm.

Using [REDACTED] Interactive Web Response Technology System (IWRS), all eligible and non-eligible patients who are consented and screened into the study will be assigned a patient number. The patient number is assigned after a patient is consented. It is the only identifier for screened patients.

[REDACTED] The system will also assign a study product kit number (based on the randomization schedule created by an independent biostatistician). The study product kit number is the identifying number listed on the study product dispensed to eligible patients. The study product kit number is a five-digit number. This will be the identifier used for randomized patients (i.e., randomization number). Both the patient number and randomization number will be entered into the patient's eCRF. At the end of the study, after all the clinical data have been entered and the study database has been locked, a copy of the randomization schedule will be sent to the statistician.

The Investigator, staff at the study site, study monitors, and data analysis/management personnel will be blinded to the patient assignment.

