5. SAMPLE SIZE

For the primary endpoint analysis (proportion of index patients in the PP population who are considered to be a Treatment Success on Day 15 ± 2), sample size is estimated for therapeutic equivalence of the Test to the Reference product and superiority of each of the active treatments groups over Placebo. The sample size estimations are based on data reported in the product label for SKLICE® (ivermectin) Lotion, 0.5%.

STATISTICAL ANALYSIS PLAN

Ivermectin Lotion 0.5%

Protocol / Study No. 71691702

Under the above assumptions, [REDACTED]

may be randomized

approximately 364 index patients

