7. EFFICACY ENDPOINTS

Primary Efficacy Endpoint

The primary efficacy endpoint is the proportion of index patients in each treatment group who are considered a Treatment Success on Day 15 ± 2 . Treatment Success is defined as the absence of live lice.

Secondary Efficacy Variable

The secondary efficacy endpoint is the proportion of all randomized patients (i.e., index + non-index) who are considered a Treatment Success on Day 15 ± 2 . Treatment Success is defined as the absence of live lice.

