Placebo: Placebo (vehicle) lotion (Actavis Laboratories UT, Inc.)

OUTPUT: L:\DEV\917\71691702\SAS\OUT\XXXX

Created on: ddmmmyy hh:mm

Page 1 of N

STATISTICAL ANALYSIS PLAN

Ivermectin Cream 0.5%

Protocol / Study No. 71691702

T16.1.9.10 Summary of Frequency of All Adverse Events by Body System (Safety Population)

Body System	MedDRA Term	Test (N = xxx)		Reference (N = xxx)		Placebo (N = xxx)		Fisher's P-value
		Events	Patients	Events	Patients	Events	Patients	
Patient with at least one AE	Total	xx	xx (xx.x%)	xx	xx (xx.x%)	xx	xx (xx.x%)	x.XXXX
Ear and labyrinth disorders	Ear pain	xx	xx (xx.x%)	xx	xx (xx.x%)	xx	xx (xx.x%)	x.XXXX
	etc.							
	etc.							

Comparison of treatment groups is with respect to the number of patients with at least one occurrence of the AE.

Test: Ivermectin Lotion, 0.5% (Actavis Laboratories UT, Inc.)

Reference: SKLICE® (ivermectin) Lotion, 0.5% (Arbor Pharmaceuticals, LLC)

Placebo: Placebo (vehicle) lotion (Actavis Laboratories UT, Inc.)

OUTPUT: L:\DEV\917\71691702\SAS\OUT\XXXX

Created on: ddmmmyy hh:mm

Page 1 of N

STATISTICAL ANALYSIS PLAN

Ivermectin Cream 0.5%

Protocol / Study No. 71691702

T16.1.9.11 Summary of Frequency of All Adverse Events by Severity (Safety Population)

Body System	MedDRA Term	Test			Reference			Placebo		
		# Events			# Events			# Events		
		(N=xx)			(N=xx)			(N=xx)		
Total AEs	Total AEs	xx(xx.x%)	xx(xx.x%)	xx (xx.x%)	xx(xx.x%)	xx(xx.x%)	xx (xx.x%)	xx (xx.x%)	xx (xx.x%)	xx (xx.x%)
Ear and labyrinth disorders	Ear pain	xx(xx.x%)	xx(xx.x%)	xx (xx.x%)	xx(xx.x%)	xx(xx.x%)	xx (xx.x%)	xx (xx.x%)	xx (xx.x%)	xx (xx.x%)
	Hypoacusis	xx(xx.x%)	xx(xx.x%)	xx (xx.x%)	xx(xx.x%)	xx(xx.x%)	xx (xx.x%)	xx (xx.x%)	xx (xx.x%)	xx (xx.x%)

etc.

N = Total number of events in each treatment group; Percentage is based on total number of events.

Test: Ivermectin Lotion, 0.5% (Actavis Laboratories UT, Inc.)

Reference: SKLICE® (ivermectin) Lotion, 0.5% (Arbor Pharmaceuticals, LLC)

Placebo: Placebo (vehicle) lotion (Actavis Laboratories UT, Inc.)

OUTPUT: L:\DEV\917\71691702\SAS\OUT\XXXX

Created on: ddmmmyy hh:mm

Page 1 of N

STATISTICAL ANALYSIS PLAN**Ivermectin Cream 0.5%****Protocol / Study No. 71691702****T16.1.9.12 Summary of Frequency of All Adverse Events by Relationship
(Safety Population)**

Body System	MedDRA Term	Test		Reference		Placebo	
		# Events		# Events		# Events	
		Related	Not Related	Related	Not Related	Related	Not Related

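### AE frequencies are tested patient by patient although whole households share an arm, so the Fisher p-values run too small if AEs correlate within households

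*SAP*

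**What the plan says.** **Unit of assignment.** SAP 4: "All enrolled members of a household will be randomized to the same treatment arm".

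**Who is analysed.** Protocol 11.3.3: "The Safety population will include all patients who are randomized and received study product". Non-index household members are among them, because SAP 7 describes the secondary endpoint as "the proportion of all randomized patients (i.e., index + non-index"). SAP 8.3 bases all safety analyses on this population.

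**Household size.** Protocol 10.3.2 excludes a household with "More than three members of the household infested with lice", and participating members must themselves have live lice (Protocol 10.3.1). A household therefore contributes one to three patients.

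**The test.** SAP 8.3.1: "Adverse event frequencies will be compared between treatments using" Fisher's exact test. A significant overall result leads to a Test-Reference test, which is meant to show whether the difference is due to the active product. The shell for T16.1.9.10 in SAP 9 prints a p-value per MedDRA term and confirms the unit: "Comparison of treatment groups is with respect to the number of patients with at least one occurrence of the AE".

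**What is absent.** Neither document mentions household clustering in the safety analysis. SAP 8.4 makes no multiplicity adjustment.

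**The concern.** Fisher's exact test takes its reference distribution from shuffling individual patients between arms. In this trial only households could have changed arm. Members of a household share an environment and intercurrent illnesses, which Protocol 10.7.1 counts as AEs. An adult also completes the diary for younger members (Protocol 10.6.13). Positive correlation within households is therefore plausible. If it exists, the number of affected patients per arm varies more than the test allows for, and small p-values appear too often.

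At stake is the third study objective, the safety comparison. A chance cluster of illness in a few households could be reported as a treatment difference and, through the second step, as a difference between the generic and the reference product.

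**Working it through.** The plan states no AE rate, ICC, household-size mix or safety error rate, so there is no figure of its own to reproduce.

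**Inputs from the documents**
- Households: one index patient each. The Protocol synopsis says "of which approximately 378 are expected to be index patients"; SAP 5, written from the earlier protocol revision, says "approximately 364 index patients". The check uses 378.
- Household size: 1 to 3.
- Two-sided 5% level; Test-Reference test only after a significant overall test.

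**Assumptions, not in the documents**
- Equal allocation (the ratio is blacked out): 378 / 3 = 126 households per arm.
- Equal shares of one-, two- and three-member households.
- AE rate 10-20%, the same in every arm.
- ICC 0 to 0.4.

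**Step 1: design effect.** With household size m, the variance of an arm's AE count is multiplied by DE = 1 + (E[m²]/E[m] − 1) × ICC.
- Equal mix: E[m] = (1+2+3)/3 = 2 and E[m²] = (1+4+9)/3 = 4.667, so DE = 1 + (2.333 − 1) × ICC = 1 + 1.333 × ICC.
- Upper limit, every household with three patients: DE = 1 + 2 × ICC.

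**Step 2: rejection rate under no true difference.** Simulated, following the SAP's sequence:

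| ICC | DE | Overall three-arm test | Test-Reference after significant overall test |
|---|---|---|---|
| 0 | 1.00 | about 4-5% | about 2% |
| 0.1 | 1.13 | 6-6.5% | 3% |
| 0.2 | 1.27 | 9-10% | 5-6% |
| 0.4 | 1.53 | 13% | 6-8% |

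**Step 3: rare terms and small households.**
- AE rate 1%, equal size mix, overall test (3,000 beta-binomial trials per scenario, allocation 1:1:1 or 2:2:1): 2.8-3.7% at ICC 0, 3.9-5.8% at 0.1 and 6.5-9.2% at 0.3.
- AE rate 1%, equal size mix, Test-Reference in sequence (2,000 trials per scenario): at most 3.9% up to ICC 0.4.
- AE rate 1%, mostly single-patient households (70% one, 20% two, 10% three; mean 0.7 + 0.4 + 0.3 = 1.4): overall test 4.8-5.3% at ICC 0.1-0.2, Test-Reference in sequence about 1%.

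Fisher's own conservatism with sparse counts absorbs most or all of the excess when the ICC is low.

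**Step 4: does the remedy work?** With the equal mix, AE rates of 3% or 10% and 1,200 trials per scenario, the planned overall Fisher test rejected in 4-6% at ICC 0, 6-8% at 0.1, 12% at 0.3 and 16-17% at 0.5. A household-level permutation of the same comparison rejected in 4-6% at every ICC. The Monte Carlo standard error near 5% is √(0.05 × 0.95 / 1200) = 0.6 points, so 4-6% is compatible with the nominal level. The permutation version of the Test-Reference step was not simulated. It rests on the same argument, that households are exchangeable between arms when there is no difference.

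**The case against.** Five points can be made for leaving the plan as it is.

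- **Nothing is decided on these p-values.** Equivalence and superiority rest on the primary endpoint in index patients, one per household. This stands and is the main reason the point is minor.
- **The size is unknown.** With at most three patients per household and no ICC in the documents, nobody can say in advance that the p-values are too small. This stands. A reader might infer that they certainly are, but the documents support only the conditional statement.
- **The Test-Reference comparison is protected by the overall test.** This largely stands. A reader might infer that false Test-Reference differences generally exceed 5%. That follows only if the pairwise test is run on its own: at ICC 0.3 it then rejects in 8.0% of trials (equal mix, AE rate 10%, 126 households per arm), against about 6% in the planned sequence. In sequence, the rate stays below 5% at ICC 0.1, is at about 5-6% at ICC 0.2 and rises modestly above that.
- **The p-values are exploratory.** Protocol 11.8 makes the testing depend on having enough data, local reactions and ocular discomfort are compared descriptively, and a false signal does not hide harm. This stands in part. However, SAP 8.3.1 drops the Protocol's condition and uses the Test-Reference result to attribute a difference to the active product, which is an inference.
- **A cluster-adjusted chi-square such as Rao-Scott suits sparse per-term counts poorly.** This stands, and that option is not recommended here.

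**Conclusion.** The mismatch between unit of assignment and unit of analysis follows directly from the text and needs no assumption. Its effect is conditional: the AE tests are anticonservative if AEs correlate positively within households. Under the assumed inputs the excess falls mainly on the overall three-arm test, roughly double its nominal level at ICC 0.2 (9-10%) and 13% at 0.4. The Test-Reference step as planned is affected much less. At low ICC the excess is small for terms near 1% or where most households contribute one patient; at ICC 0.3 even a 1% term shows 6.5-9.2% on the overall test with the equal size mix.

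A reader might also infer that this threatens the equivalence or superiority conclusions. It does not, because neither uses these tests. The consequence is limited to false AE signals under the safety objective. Severity: minor.

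**What to change.** In SAP 8.3.1, keep the two-step sequence but obtain both p-values, overall and Test-Reference, by permuting arm labels between households so that all members of a household move together. If the randomisation schedule was blocked or stratified, permute within the same blocks or strata. Amend the note under T16.1.9.10 to name the household as the unit permuted. Keep all AE counts and percentages by patient as planned.

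Protocol 11.8 already allows a test comparable to Fisher's, so no protocol amendment is needed. The cost is a paragraph in the SAP, a small programming change and a household identifier in the analysis dataset, with slightly less sensitivity per AE term.

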11.8 Safety Analysis

Adverse events will be classified using standard Medical Dictionary for Regulatory Activities (MedDRA) terminology Version 20.0 or higher and summarized by treatment group. Summary tables comparing the type, date of onset, date of resolution, incidence, severity, relationship to the study product, action taken, and outcome will be prepared by treatment group. If sufficient data exist, then AE frequencies will be compared among treatments using Fisher's exact test or a similar test. Application site reactions and ocular discomfort will be compared descriptively among treatment groups.

Concomitant medication use during the randomized treatment period will be tabulated by patient.

Signs and symptoms of head lice will not be considered AEs, unless in the Investigator's opinion, they have increased in frequency and/or severity to such an extent that the Investigator/patient considers to be clinically significant.

All patients who received randomized treatment and received study product will be included in the comparative safety analysis.

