8. STATISTICAL ANALYSIS METHODS

If not otherwise specified, statistical significance is defined as $p < 0.05$ and is two-tailed. Data will be summarized with respect to demographic and baseline characteristics, efficacy variables and safety variables.

For categorical variables, the number and percent of each category within a parameter will be calculated for non-missing data. For continuous variables, statistics will include number of observations, mean, standard deviation, median, minimum and maximum values.

All statistical analyses will be conducted using SAS[®], Version 9.4 or higher. Datasets will be prepared using headings from Clinical Data Interchange Consortium (CDISC) Study Data Tabulation Model (SDTM) implementation for human clinical trials and ADaM (Analysis Dataset Model). ADaM datasets will include but not limited to ADSL, ADEFF, ADAE, ADVS, ADCM and ADMH.

STATISTICAL ANALYSIS PLAN

Ivermectin Lotion 0.5%

Protocol / Study No. 71691702

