8.3.2 Application Site Reactions

The following application site reactions will be evaluated at each visit based on the scale provided below:

Signs and Symptoms:

Erythema

Pyoderma

STATISTICAL ANALYSIS PLAN

Ivermectin Lotion 0.5%

Protocol / Study No. 71691702

Excoriation
Pain
Pruritus
Edema

Grading Scale:

Absent	0	
Mild	1	(slight, barely perceptible)
Moderate	2	(distinct presence)
Severe	3	(marked, intense)

Application site reactions and ocular discomfort will be compared descriptively among treatment groups. A frequency summary table comparing the application site reactions for each treatment group will be presented by visit.

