8.4 Multiple Comparisons

No multiple comparison adjustment will be made in this study.

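### Adverse-event Fisher tests are unadjusted and not labelled descriptive, and their follow-up test is given an attribution it cannot support

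*SAP*

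**What the plan says.** SAP 8.3.1 states without condition: "Adverse event frequencies will be compared between treatments using Fisher’s exact test". It then adds a gated step: "If the overall Fisher’s test is statistically significant, a pairwise test will be conducted for Test and Reference to determine if the difference in AEs". The stated purpose of that step is to attribute such a difference to the active.

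Shell T16.1.9.10 has three arm columns and one Fisher p-value column. That column is filled both for patients with at least one AE and for an example term (ear pain). Its footnote reads: "Comparison of treatment groups is with respect to the number of patients with at least one occurrence of the AE".

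The level comes from SAP 8: "If not otherwise specified, statistical significance is defined as $p < 0.05$ and is two-tailed". Section 8.3.1 sets no other. SAP 8.4 says: "No multiple comparison adjustment will be made in this study".

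Two other passages bear on this:
- SAP 8.3.2 does label its comparisons: "Application site reactions and ocular discomfort will be compared descriptively among treatment groups". The AE tests have no such label.
- Protocol 11.8 makes AE testing conditional: "If sufficient data exist, then AE frequencies will be compared among treatments using" Fisher's exact test or a similar one. Neither document defines the condition, and the SAP omits it.

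**The concern.** The SAP attaches a consequence to significance in the AE table, so the p-values are more than a display. Followed as written, it allows a difference on a single term to be called statistically significant, however many terms are tested.

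The follow-up test has a separate fault. Test and Reference contain the same active at the same strength. A difference between them cannot be assigned to ivermectin, and the absence of one does not clear ivermectin. Attribution to the active would need the comparisons with Placebo, which the follow-up rule does not include.

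At stake is Objective 3, the comparison of safety across the three products. A chance result on one term could be reported as a safety difference for a generic intended to be equivalent, or credited to the wrong cause.

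**Working it through.** The documents state no error rate for the AE tests, so there is no figure to reproduce. The question is what the rule yields when the three products have identical AE risk.

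**Inputs from the documents.** Three arms; two-sided 0.05 per test (SAP 8); no adjustment (SAP 8.4); about 378 index patients (protocol synopsis; the SAP, written from protocol Rev. 0, has about 364). The Safety population also includes non-index patients, and its size is not given.

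**Assumptions.** Allocation is redacted, so equal arms are assumed: 378/3 = 126, or 200 to allow for non-index patients. The number of terms K and the incidence per term are not given; 10 or 20 terms at 0.25% to 3% are shown. Terms are treated as independent.

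**Step 1: size of one three-arm test.** For each total m of patients with the term, enumerate all 3×2 tables, find those with Fisher p < 0.05, and average their probability over m ~ Binomial(3n, incidence). Call this s.

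**Step 2: both steps.** Keep only those tables where the Test versus Reference Fisher test also gives p < 0.05. Call this b.

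**Step 3: at least one false result over K terms.** 1 − (1 − s)^K for the three-arm test; 1 − (1 − b)^K for both steps. Example, n = 126, incidence 1%, K = 20: 1 − (1 − 0.01145)^20 = 20.6%, and 1 − (1 − 0.00103)^20 = 2.0%.

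| n per arm | Incidence | s | b | Three-arm, K=10 | Three-arm, K=20 | Both steps, K=10 | Both steps, K=20 |
|---|---|---|---|---|---|---|---|
| 126 | 0.25% | 0.05% | <0.01% | 0.5% | 1.0% | <0.1% | <0.1% |
| 126 | 0.5% | 0.33% | <0.01% | 3.3% | 6.5% | <0.1% | 0.1% |
| 126 | 1% | 1.15% | 0.10% | 10.9% | 20.6% | 1.0% | 2.0% |
| 126 | 2% | 2.68% | 0.80% | 23.8% | 42.0% | 7.7% | 14.8% |
| 126 | 3% | 3.79% | 1.34% | 32.0% | 53.8% | 12.6% | 23.7% |
| 200 | 0.25% | 0.19% | <0.01% | 1.9% | 3.8% | <0.1% | <0.1% |
| 200 | 0.5% | 0.84% | 0.04% | 8.1% | 15.5% | 0.4% | 0.8% |
| 200 | 1% | 1.99% | 0.46% | 18.2% | 33.1% | 4.5% | 8.8% |
| 200 | 2% | 3.53% | 1.30% | 30.2% | 51.3% | 12.2% | 23.0% |
| 200 | 3% | 4.05% | 1.64% | 33.9% | 56.3% | 15.2% | 28.1% |

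The low rows reflect Fisher's conservatism. With these equal arms, a term seen in three or fewer patients overall cannot reach p < 0.05, and passing both steps needs at least six.

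**Sensitivity.**
- *Correlation.* With correlation 0.5 between tests at 1% to 3% incidence, the three-arm figure falls to 7.5%–21% for 10 terms and 12%–30% for 20.
- *Allocation.* Under 2:2:1 with 378 patients it rises for rare terms: 20 terms give 15% at 0.25% incidence and 27% at 0.5%.
- *Few terms.* Five terms at 1% with n = 126 give 1 − (1 − 0.01145)^5 = 5.6%.
- *Clustering.* Household members share an arm (SAP 4). The calculation ignores this; it could raise the error if AEs cluster within households.

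**The case against.** A reader might infer that a false safety difference is likely. The documents do not support that: they give neither the number of terms nor their rates. In the table the three-arm figure passes 50% only with 20 independent terms at 2% to 3%. Twenty terms at 3% would mean 20 × 0.03 = 0.6 term reports per patient in about two weeks after one 10-minute application. For sparse terms the excess is small or absent.

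Nor is it established that every significant term triggers the follow-up. SAP 8.3.1 speaks of the overall test in the singular, which may mean only the any-AE row. The shell has no pairwise column, and SAP 9 presents the shells as a general layout. On the narrow reading the trigger is one test of size at most 5%, given independent patients, and the both-steps figures over K terms do not apply. On the wider reading the first step still screens the second, so a false Test versus Reference difference is much rarer than a false three-arm signal.

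The protocol's sufficient-data condition would also reduce the number of tests, and SAP 1 encourages readers to consult the protocol.

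These arguments limit the size of the problem. They do not supply a descriptive label, settle the trigger, define the condition or make the attribution valid.

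**Conclusion.** The point holds as an uncontrolled false-signal rate together with an invalid attribution. At 1% to 3% incidence and 20 terms, the chance of at least one false three-arm signal is 21% to 56%; at 0.25% to 0.5% it is 1.0% to 15.5%. If each row can trigger the follow-up, a false Test versus Reference difference at 1% to 3% incidence passes both steps in about 1% to 15% of trials with 10 terms and 2% to 28% with 20. These ranges rest on equal arms of 126 to 200, identical risks and independent terms.

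The attribution fault depends on none of these assumptions: comparing two 0.5% ivermectin lotions cannot show that a difference is due to ivermectin.

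The equivalence and superiority conclusions are not at risk. Both rest on the primary efficacy endpoint alone (protocol 11.6, SAP 8.2.1), and no AE test enters them. The consequence is confined to how the safety tables may be read under Objective 3.

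**What to change.** Amend the SAP as follows:

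- **8.3.1, trigger.** State that only the any-AE row is read at the 5% level and that only this row triggers the follow-up.
- **8.3.1, purpose.** Replace the attribution wording with a plain Test versus Reference comparison. Any statement about the active product should rest on the comparisons with Placebo.
- **8.3.1, condition.** Restore the protocol's sufficient-data condition and define it, for example as a minimum total number of patients with the term.
- **T16.1.9.10.** Add a footnote that per-term p-values are descriptive. If per-term differences with 95% confidence intervals are added, name the pair compared and mark them descriptive too; otherwise an interval excluding zero would bring back the same unadjusted reading.
- **8.4.** Add: *AE p-values other than for the any-AE row are descriptive, and no conclusion of a treatment difference is drawn from them.*

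The cost is SAP wording and a footnote, plus a column if intervals are shown. No further data or patients are needed. The downside is that no single AE term can be called statistically significant, though every term stays on display.
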